	Placebo: Saline Solution 0.9%						
	Dose: N/A						
	Route: Intravenous						
	Regimen: Weeks 0, 4, 8, 16, 24 and 32.						
Duration of administration	1 hour						
Laboratory Samples.	Screening, Week 0, 24 and 52.						
Visits by Weeks	Screening						
	Week 0 – Infusion 1						
	Week 4 – Infusion 2						
	Week 8 – Infusion 3						
	Week 16 – Infusion 4						
	Week 24 – Infusion 5						
	Week 32 – Infusion 6						
	Week 42 – Follow Up.						
	Week 52 – End of Study						

"A Randomized, Double-Blind, Single Center, Phase 2, Efficacy and Safety Study of autologous HB-adMSCs vs Placebo for the Treatment of Patients with Parkinson's Disease"

Introduction

Objectives

Primary Objective:

• To investigate the safety and efficacy of intravenous infusions of HB-adMSCs vs Placebo in patients with Parkinson's disease as determined by improvements in Quality of Life as measured by the MDS UPDRS assessment. (Time frame: Baseline to Weeks 4, 8, 16, 24, 32, 42 and 52).

Secondary Objective:

• To evaluate the safety and efficacy of intravenous infusions of HB-adMSCs vs Placebo in patients with Parkinson's disease as, determined by changes in disease assessments and dosage of medications. (Time frame: Baseline to Weeks 4, 8, 16, 24, 32, 42 and 52).

Endpoints

Primary Endpoints

The safety and efficacy endpoints of this study will be evaluated by assessing changes from Baseline to Weeks 52 in the following:

- Changes in MDS-UPDRS Part II from Baseline to Week 52. Motor Aspects of Experiences of Daily Living (M-EDL), including speech, saliva and drooling, chewing and swallowing, eating tasks, dressing, hygiene, handwriting, doing hobbies and other activities, turning in bed, tremor, getting out of bed, a car, or a deep chair, walking and balance and freezing.
- Incidence of treatment-emergent Adverse Event (TEAEs) and serious Adverse Events (SAEs).
- Incidence and risk of AEs of special interest (serious or nonserious), including thromboembolic events, peripheral events defined as, thromboembolism of the extremities, also infections and hypersensitivities.
- Clinically significant changes in laboratory values, vital signs, weight and physical examination results.

Secondary Endpoints

The safety and efficacy endpoints of this study will be evaluated by identifying changes from Baseline to Weeks 4, 8, 16, 24, 32, 42 and 52 in the following:

- Changes in MDS-UPDS Part I, III, IV, or total score.

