- Changes Neuro-Quality of Life Assessments, including Communication, Ability to Participate in Social Roles and Activities, Anxiety, Depression, Emotional and Behavioral Dyscontrol, Fatigue, Lower Extremity Function (Mobility), Positive Affect and Well-Being, Sleep Disturbance, Upper Extremity Function (Fine Motor, ADL), Stigma, Satisfaction with Social Roles and Activities and Cognition Function.
- Changes in Parkinson's disease fatigue scale (PFS-16). Score of ≥8 indicates the presence of significant fatigue.
- Changes in Parkinson's disease Questionnaire (PDQ-39), assessing how often patients experience difficulties across the 8 quality of life dimensions of functioning of well-being.
- Changes in Visual Analog Scale for Pain and muscle spasms.
- Changes in Dosage of medications taken to treat Parkinson's disease.
- Incidence of treatment-emergent Adverse Event (TEAEs) and serious Adverse Events (SAEs).
- Incidence and risk of AEs of special interest (serious or nonserious), including thromboembolic events, peripheral events defined as, thromboembolism of the extremities, also infections and hypersensitivities.
- Clinically significant changes in laboratory values, vital signs, weight and physical examination results.

Investigational Plan.

This is a randomized, double-blind, single center, phase 2 study to assess efficacy and safety of multiple HB-adMSCs vs Placebo for the treatment of Parkinson's disease.

The trial includes a screening period of up to 4 weeks, a 32-week treatment period, and a safety Follow-up period of 20 weeks after the last investigational product administration.

This clinical trial will be open to enroll 24 eligible participants diagnosed with Parkinson's disease. Patients' recruitment will be conducted by the study team, if eligible participants are identified based on eligibility criteria, a screening visit will be scheduled. Informed consent form will be given to the study participants and signed before any study procedures. Informed consent

Confidential

form will include information about the clinical trial and some aspects should be considered during this process.

After Informed consent has been obtained, each participant should complete the following visits.

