Unblinded pharmacist, also identified as Mixer, will keep records of the treatment assigned to each subject in the unblinded pharmacy binder. Access to this pharmacist binder will be limited to the unblinded pharmacist.

Blinding for Clinical Evaluators

To minimize assessment bias, clinical evaluators (data analysts and physicians) will be trained on how to maintain blinding to treatment as best as possible. "Best as possible" means that blinding will be maintained unless an adverse event or serious adverse events occurs that requires unblinding the physician, which is determined by the medical monitor or DSMB.

Training includes review of the process of blinding, describing who will be responsible for assigning product for the appropriate group, labels that will be used to identify subjects but not treatment group, and the process that should be followed if an adverse event occurs, triggering review by medical monitor and/or DSMB.

Prior and Concomitant Medications

Concurrent and prior medications (up to one week before the screening visit) should be recorded in the subject's medical history at the screening visit. This list of concomitant medications may be updated if necessary, at the following visits.

It is important to ask the subject about the start and end date of the current and prior medications, if the subject does not remember the specific date or month, it is recommended to include the approximate year to give an estimate of how long the patient has been taking the medication.

Trial Procedures

The trial includes a up to 28 days screening period, a 32-week Treatment Period and a 20-week Safety Follow-up Period. All periods are associated with evaluations and procedure that must be performed at specific time points as represented in Table 3 Schedule of Assessments.

Trial Schedule of Assessments.

Table 3 Schedule of Assessments.

	Visit 1	Visit 2	Visit 3	Visit 4	Visit 5	Visit 6	Visit 7	Visit 8	Visit 9										
Visit Names Window Period Visit Weeks	Screening Up to 28 days N/A	INF 1 + 7 days 0	INF 2 + 7 days 4	INF 3 + 7 days 8	INF 4 + 7 days 16	INF 5 + 7 days 24	INF 6 + 7 days 32	Follow Up + 7 days 42	EOS + 7 days 52										
										Informed Consent	•								
										Demographics	•								
Medical History	•	•	•	•	•	•	•	•	•										
Concomitant Medications	•	•	•	•	•	•	•	•	•										
Eligibility Criteria	•	•																	
Vital Signs	•	•	•	•	•	•	•	•	•										

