Weight	•	•	•	•	•	•	•	•	•										
Height	•																		
Laboratory Samples ¹	•	•				•			•										
Physical Examination	•	•	•	•	•	•	•	•	•										
Parkinson's Disease Assessments ²	•	•	•	•	•	•	•	•	•										
Study Treatments Administration		•	•	•	•	•	•												
24 hours Telephone Encounter		•	•	•	•	•	•												
Video Documentation	•	•				•			•										
AE and SAE assessments		•	•	•	•	•	•	•	•										

2. Parkinson's disease Assessments – MDS-UPDRS, VAS pain and muscle spasms, Neuro-Quality of Life Assessments, Parkinson's disease fatigue scale (PFS-16) and Parkinson's disease Questionnaire (PDQ-39).

Study Visits 1 to 9.

Visit 1 – Screening.

At the Screening Visit (Visit 1), study participants' information will be collected by study's delegated personnel for evaluation of trial eligibility. The following information is required to determine eligibility:

- Signing Informed Consent Form (prior to any trial-related activities).
- Collection of demographic information, such as age, race, ethnicity, date of birth, gender and relevant medical and surgical history.
- Collection of Medical History and concomitant medications, including relevant information about the past and present health of study participants.
- Inclusion and Exclusion criteria evaluation.
- Measurement of vital signs including respiratory rate, body temperature, blood pressure, pulse rate, oxygen saturation, weight and height.
- Collection of laboratory samples, including Comprehensive Metabolic Panel (CMP), Complete Blood Count (CBC), Coagulation Panel and Urine pregnancy test if female of childbearing potential.
- Physical examination by Principal Investigator, including clinical assessments such as MDS-Unified Parkinson's Disease Rating Scale and other assessments included in Table 3.
- Completion of neuro-quality of life questionnaire by study's participant and handwriting assessments.
- A video documenting study participant walking and standing from sitting will be recorded during this visit.

Within 28 days of the Visit 1 - Screening, the principal investigator must make a decision to determine participant's eligibility. Once, the eligibility of the subject has been confirmed by the principal investigator, the randomization process will be conducted.

Visit 2 – Infusion 1 (Baseline)

The following procedures are required during this visit:

- Reconfirm eligibility criteria.
- Update medical history and concomitant medications if any change occurred since last visit.

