Assessments Related to Endpoints

MDS-Unified Parkinson's Disease Rating Scale

The MDS-UPDRS scale refers to Movement Disorder Society - Unified Parkinson Disease Rating Scale, and it is a rating tool used to gauge the course of Parkinson's disease in patients. Each answer to the scale is evaluated by the principal investigator during the study visit. Some sections of the MDS-UPDRS scale require multiple grades assigned to each extremity.

Physical Examinations

A complete physical examination will be performed by the principal investigator or delegated sub-investigator, including general appearance, head, eyes, ear, nose, and throat (HEENT), neck, cardiovascular, thorax/lungs, abdomen, genitourinary, musculoskeletal, lymph nodes, skin,

neurological and mental status examination, height (at Screening only), and body weight at Visits 1, 2, 3, 4, 5, 6, 7, 8 and 9.

The principal investigator or delegated sub-investigator will evaluate the clinical significance of abnormal findings identified during physical examinations. Pre-existing conditions diagnosed through assessments and examinations at the screening visit or during the screening period are not adverse events but are recorded as medical history. If any clinically significant abnormal findings are discovered after informed consent or any pre-existing conditions worsen during the trial, these must be recorded as adverse events.

Vital Signs

Vital signs will be measured at Visits 1, 2, 3, 4, 5, 6, 7, 8 and 9 and will include respiratory rate, pulse rate, blood pressure (measured after the study participant has been in a seated position for more than 5 minutes of rest), body temperature and oxygen saturation. Clinical significance of any abnormal result must be evaluated by principal investigator. Clinically significant abnormal findings will be reported as adverse events.

Clinical Safety Laboratory Parameters

The following laboratory parameters should be collected at Visit 1, 2, 6 and 9.

- Comprehensive Metabolic Panel, also known as CMP or Chemistry Panel is a group of different tests that measure several substances in the study's participant blood.
- Complete Blood Count, also known as CBC, hemogram or CBC with Differential is a group of tests that evaluate the cells that circulate in blood, including red blood cells (RBCs), white blood cells (WBCs), and platelets.
- Coagulation Tests including Prothrombin Time (PT or PT-INR) to identify any coagulation disorder during study participation.

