- Urine Pregnancy Test, a urine sample, preferably collected during morning time, to confirm pregnancy during study participation. This test will be limited to Women of Childbearing Potential (WOCBP)

Other Assessments

Demography

Demographic data will be collected at the Screening Visit, including age, race, ethnicity, date of birth and gender.

Medical and Surgical History

Medical information on any previous concomitant illnesses, other than Parkinson's disease should be collected during Screening Visit and updated if needed during the following study

visits. For planned procedures/hospitalizations during the clinical trial, documentation should be completed at the time of the Screening.

Parkinson's disease and Previous Therapy for this disease

The date of diagnosis of Parkinson's disease, as well as previous treatments, will be recorded during Screening visit.

Concomitant Medication Review

Data concerning concomitant medications and procedures will be collected throughout the clinical trial. This data will be obtained at scheduled or unscheduled visits based on information provided by the patient.

Handling of Biological Samples

Sampling tubes, material for shipments of the samples and a laboratory manual detailing all sample collection and shipment procedures will be provided and distributed to the clinical trial site by the selected laboratory. Laboratory samples will be collected as per protocol during Visit 1 – Screening, and/or Visit 2 – Infusion 1 (Baseline), Visit 6 - Infusion 5 and Visit 9 – End of Study.

Adverse Events

Adverse Event

An *adverse event* (AE) is any symptom, sign, illness or experience that develops or worsens in severity during the course of the study. Intercurrent illnesses or injuries should be regarded as adverse events. Abnormal results of diagnostic procedures are considered as adverse events if the abnormality results in study withdrawal, a serious adverse event, leads to additional treatment or diagnostic tests, or is considered by the investigator to be of clinical significance. Information on all adverse events should be recorded immediately in the source documents, CRF and in the appropriate adverse event section of the source documents. All clearly related signs, symptoms, and abnormal diagnostic procedures results should be recorded in the source document and CRF, though should be grouped under one diagnosis.

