A repeat measure mixed model will be used to assess within-subject changes from baseline. correction for multiple comparisons will be employed for post-hoc comparisons. Parkinson's assessment scores (i.e., MDS-UPDRS) at screening and infusion 1 (before treatment) will be averaged and treated as a baseline. Averaging is performed to minimize sources of variance (i.e., patient condition, assessors) and particularly to establish a reliable baseline from which to establish changes.

Data Handling Case Report Forms (CRF)

As used in this protocol, the term CRF should be understood to refer to either a paper form or an electronic data record or both. Reports received by the site, or from the central laboratory should be printed, retained as source documentation and signed by the principal investigator, indicating which values are considered clinically significant and to be reported as AEs if applicable.

Source data is all information, original records of clinical findings, observations, or other activities in a clinical trial necessary for the reconstruction and evaluation of the trial. Source data are contained in source documents

Changes in the Conduct of the Clinical Trial Protocol Amendments

Any change to the protocol will need to have a protocol amendment submitted to the IND, and FDA and IRB must agree prior to proceeding.

Deviations from the Protocol

Deviations from the protocol should not occur. If safety deviations occur, the principal investigator must inform the Monitor, and the implications of the deviations must be reviewed and discussed. Any deviation must be documented in the protocol deviation log. In addition, each deviation must include a description of the deviation, the relevant dates (start and stop), and the action taken. All deviation reports and supporting documents must be kept in the Investigator Site File and in the Trial Master File.

Premature Clinical Trial Termination

Both the Study Investigator and Sponsor have the right to terminate the clinical trial at any time. Should this become necessary, the procedures will be agreed upon after consultation between the two parties. In terminating the clinical trial, the Sponsor and the Study Investigator will ensure that adequate consideration is given to the protection of the best interests of the study participants. Regulatory authorities and IRB will be informed.

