7.2. Secondary Efficacy Analyses

7.2.1. Endpoints / Variables

Difference between the Baseline value and the value measured at all the timepoints collected, during the period of study (52 Weeks), at Weeks 4, 8, 16, 24, 32, 42 and 52 visits for below efficacy measures:

- MDS-UPDRS total score
- Total MDS-UPDRS score for Part I
- Total MDS-UPDRS score for Part II
- Total MDS-UPDRS Part III Score
- Total MDS-UPDRS Part IV Score
- Total Neuro-Quality of Life Assessments scores (Neuro-QOL)
- Total Parkinson's disease fatigue scale (PFS-16) Score
- Total Parkinson's disease Questionnaire (PDQ-39) Score
- Visual Analogue Scale (VAS) Score
- Muscle Spasm Scale VAS Score
- Pain Scale VAS score

• Daily dose of Medication to treat Parkinson's Disease

Proportion of subjects requiring reinstatement of PD medication dose following reduction in dose during the study.

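### The plan sets no medication state, time since last Parkinson's dose or time of day for MDS-UPDRS ratings, which leaves avoidable noise in the exploratory Part III and total-score changes

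*Protocol*

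**What the plan says.** **Rating.** Under Trial Assessments the protocol says of the MDS-UPDRS that "Each answer to the scale is evaluated by the principal investigator during the study visit". The note to Table 3 lists "Parkinson's disease Assessments – MDS-UPDRS, VAS pain and muscle spasms, Neuro-Quality of Life Assessments, Parkinson's disease fatigue scale (PFS-16" among the Parkinson's assessments, and the table marks these at Visits 1 to 9.

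**Endpoints.** The protocol's secondary endpoints include "Changes in MDS-UPDS Part I, III, IV, or total score", and SAP 7.2.1 lists "Total MDS-UPDRS Part III Score". SAP 2.3 calls all secondary endpoints exploratory. SAP 5.4 puts Part III at Week 52 in an eight-endpoint Holm family that does not include the total score. The primary efficacy endpoint is Part II at Week 52.

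**Medication.** The severity stratum in the randomization section uses daily carbidopa/levodopa dose, for those taking it. A further secondary endpoint is "Changes in Dosage of medications taken to treat Parkinson's disease". On collection, the protocol says "Data concerning concomitant medications and procedures will be collected throughout the clinical trial" and, on detail, "It is important to ask the subject about the start and end date of the current and prior medications".

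**Baseline.** The protocol's Statistical Methods section averages the screening and infusion 1 scores and gives the reason: "Averaging is performed to minimize sources of variance (i.e., patient condition, assessors" being the sources named. SAP 5.2 instead takes the single latest non-missing pre-treatment value.

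**The concern.** A Part III score comes from examining the patient. If that score depends on whether the last dose is still working (ON) or has worn off (OFF), a participant seen soon after a dose at baseline and long after one at Week 52 can appear to have worsened with no change in the disease. The protocol accepts the general point by naming patient condition as a variance source.

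The visit structure makes a shift in rating time plausible. Visits 2 to 7 contain an infusion of about one hour and two hours of monitoring; Visits 8 and 9 contain neither. The baseline rating is placed before treatment, but no text says whether ratings at Visits 3 to 7 come before or after the infusion.

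At stake is precision in Part III and total score in a trial of 24 participants. There is a secondary risk to the comparison itself if dosing habits come to differ between arms.

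**Working it through.** **1. Is the rating state set anywhere?**

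| Item | Protocol | SAP |
|---|---|---|
| Who rates, and when | Principal investigator, Visits 1 to 9 | Not addressed |
| ON/OFF state | Not specified | Not specified |
| Time since last Parkinson's dose | Not specified | Not specified |
| Time of day | Not specified | Not specified |
| Order relative to infusion | Baseline only (before treatment) | Baseline only (5.2) |
| Medication data | Start and end dates, updates at visits | Dose changes and reinstatement (7.2) |
| Covariates | None named | Baseline, where applicable (5.3.1) |

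The medication data describe the regimen, not the state at the moment of rating.

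**2. How far can the clock move on an infusion day?** Infusion time is 250 ml ÷ 5 ml/min = 50 min to 250 ml ÷ 4 ml/min = 62.5 min, which agrees with the stated 1 hour. Adding 2 hours of monitoring, ratings before and after these procedures would lie about 3 hours apart.

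**3. What does the averaged baseline achieve?** Assume independent visit noise with equal variance s² at each rating.

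- Single baseline (SAP 5.2): change-score noise variance = s² + s² = 2.0 s².
- Mean of two baseline ratings (protocol): s² + s²/2 = 1.5 s².
- Reduction = 1 − 1.5/2.0 = 25% of the noise variance, or 1 − √0.75 = 13% of its SD.

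The follow-up share, s², is the same either way. SAP 10.2.2.2 takes one value per post-baseline visit. Under the SAP's baseline rule the 25% reduction is lost as well.

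**4. What might the noise cost?** The plan states no power, effect size or SD, so there is no figure to reproduce. As illustration, take 12 per arm and a two-sample t-test at two-sided 0.05. The difference with 80% power is d = 1.197 SD. Suppose uncontrolled state multiplies the variance of the Week 52 change by v. Effective size per arm is then 12/v, and power is evaluated at 1.197/√v.

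| Assumed v | Effective n per arm | Standardized effect | Power at 0.05 | Power at first Holm step |
|---|---|---|---|---|
| 1.00 | 12.0 | 1.197 | 80% | 38% |
| 1.10 | 10.9 | 1.141 | 76% | 33% |
| 1.25 | 9.6 | 1.070 | 71% | 28% |
| 1.50 | 8.0 | 0.977 | 63% | 21% |

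The last column uses the first Holm threshold in SAP 5.4, 2.5%/8 = 0.3125% two-sided. Part III would face this level only if it had the smallest p-value of the eight; later steps are less strict. The planned test is Mann-Whitney (SAP 7.2.4.1), so all these t-test powers are approximations.

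**The case against.** **The forms may already capture state.** The plan adopts a named instrument, but neither its rating form nor the CRF is among the documents. A reader might infer that nothing is recorded and that analysts could never repair the problem. The documents do not support that. They show only that the protocol and SAP do not specify the information. This objection stands.

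**One rater at one site.** The protocol has the principal investigator rate every visit at a single centre. That deals with assessors, one of the two variance sources it names. It does not deal with medication state.

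**Randomization and blinding.** Chance differences in rating time fall on both arms alike, so they cost precision and do not favour either arm. A reader might infer that the Part III comparison is biased. That would need dosing changes that differ by arm, which is possible but only a hypothesis. This objection also stands.

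**Limited reach.** Part III and total score are exploratory. Levodopa exposure is unknown, since the stratum applies it only to those taking it, in early or moderate disease. A reader might extend the point to the Part II primary endpoint, but nothing in the documents shows an effect there.

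**An analysis restricted to matching visits.** It is tempting to keep only visits rated in the baseline state. That would select on a variable that arises after randomization and that treatment could affect, in at most 24 participants. SAP 10.1.2.1 excludes participants for missing data without imputation, so the restriction could also remove people from the repeated-measures ANOVA. It should not be used.

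**Conclusion.** The point holds as a design improvement that should be made. The plan identifies patient condition as variance worth reducing, yet it leaves rating state and timing unspecified at every visit, and its SAP drops the one measure the protocol took at baseline. The protocol's Statistical Methods section and SAP 5.2 contradict each other on baseline and must be reconciled.

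The consequence is avoidable noise in Part III and total-score change. It rests on the assumption that examined motor scores vary with medication state in an appreciable share of participants. The size cannot be derived from the documents. The inflation of 10% to 50% and the 80% starting point are both assumed, so a fall from 80% to 76%, 71% or 63% must not be read as the trial's expected power. At the first Holm step the same t-test starts at 38% before any inflation.

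**What to change.** **Protocol, MDS-UPDRS section and Table 3.** As far as feasible, schedule each participant's ratings at the same time of day and the same interval since the last Parkinson's dose as at baseline, and before the infusion on infusion days. The participant's own dosing stays as it is. Record clock time, time of last dose and ON/OFF state at each rating, or confirm that the rating form or CRF already captures them. The state itself is needed because, after a dose change, the same interval need not mean the same state.

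**SAP.** Reconcile section 5.2 with the protocol's averaged baseline. Summarise rating state and time since last dose by arm and visit. Describe any Part III or total-score analysis that uses these variables as exploratory, and do not restrict it to visits rated in the baseline state.

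If ratings have already been made, the sponsor should state what was captured and report the remainder as a limitation.

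**Cost.** Three CRF fields, one descriptive table and some scheduling constraint at a single site. The constraint is real on infusion days, when the product is supplied the same day after quality control, which is why matching is asked for only as far as feasible.
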